## **8. STUDY PROCEDURES**

### **8.1. Screening Phase**

#### **8.1.1. Screening/Consenting Visit**

The following procedures will be performed at the Screening Visit within 28 days prior to randomization unless otherwise noted:

- Obtain signed, written informed consent and if applicable, child assent, and parental permission
- Medical history including demographic information
- Record history related to late effect surveillance for subjects <22 years of age at the time of enrollment using the Late-Effects surveillance form ([Appendix P](#))
- Collection of transplant history, including indication
- cGVHD Diagnosis and staging (NIH) ([Appendix M](#), [Appendix N](#), and [Appendix O](#))
- Assessment for relapse/progressive disease for subjects receiving transplant for malignant disorders
- Infection surveillance
- Evaluation of Karnofsky/Lansky performance status ([Appendix C](#))
- Physical examination including, height and weight. Document Tanner stage for subjects <22 years of age (subjects ≥22 years may use prior height measurement if available in source documents) ([Appendix P](#))
- Record AEs since signing the ICF

- Record concomitant medication history including corticosteroids requirement, over-the-counter drugs, vitamins and herbs since 30 days prior to signing ICF
- cGVHD activity assessment (eg, NIH assessments [[Appendix H](#) and [Appendix J](#)]). For subjects who begin prednisone prior to randomization, cGVHD activity assessment should be completed prior to start of prednisone. If prednisone is started at the time that ibrutinib/placebo is started (Day 1) then activity assessment can be completed any time during Screening up until the day of first dose of ibrutinib/placebo (Day 1).
- Lee cGVHD Symptom Scale ([Appendix F](#))/SF-36 questionnaire ([Appendix G](#)). Perform at the same time as cGVHD assessment.
- FEV1 (see [Section 7.1.3.2](#))
- Obtain vital signs (including blood pressure, heart rate, respiratory rate, and body temperature) after the subject has rested in the sitting position for  $\geq 3$  minutes
- Obtain blood specimens for the following laboratory tests:
  - Hematology
  - Serum chemistry
  - Coagulation studies: PT/INR, aPTT
  - Hepatitis serologies/PCR
- T/B/NK sampling ([Appendix B](#))
- Biomarker sampling ([Appendix B](#))
- Obtain 12-lead ECG after the subject has been in a supine position and resting for at least 10 minutes
- Obtain serum pregnancy test for women of childbearing potential only

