#### **10.4.2. Secondary Endpoints for Efficacy**

The secondary efficacy endpoints are:

- Response rate at 24 weeks (the proportion of responders [CR or PR]) as defined by the NIH Consensus Development Project (2014)
- Duration of response (DOR) will be defined from the time of initial partial or complete response until progression of cGVHD
- Proportion of subjects with steroid dose reduction to a level of less than 0.15 mg/kg/d at 24 weeks
- Time to withdrawal of all immunosuppressants (with the exception of ibrutinib/placebo)

- Overall survival (OS) is defined as the time from randomization until death due to any cause
- Improvement in Lee cGVHD Symptom Scale scores will be compared between the two treatment arms

Proportion of subjects with improvement in overall score on the Lee cGVHD Symptom Scale and the proportion of subjects with steroid dose reduction will be analyzed using the same method for the primary efficacy endpoint. The Kaplan Meier methodology will be used to estimate the distribution of OS for each treatment group. The log-rank test will be used to compare the OS between the 2 treatment arms. Time to withdrawal of all immunosuppressants will be analyzed using the same method used for OS.

Duration of response is defined as the interval between the date of initial documentation of a response (PR or better), and the date of first documented evidence of progressive cGVHD or death for responders only. Responders will include subjects who achieve response (PR or better) based on NIH 2014 cGVHD criteria. Non-responders will be excluded from the analysis for DOR. Median duration of response will be estimated using Kaplan Meier methodology.

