**chronic GVHD Symptom Scale**

By circling one (1) number per line, please indicate how much you have been bothered by the following problems in the past month:

SKIN:		Not at all	Slightly	Moderately	Quite a bit	Extremely
1.	Abnormal skin color.....	0	1	2	3	4
2.	Rashes.....	0	1	2	3	4
3.	Thickened skin.....	0	1	2	3	4
4.	Sores on skin.....	0	1	2	3	4
5.	Itchy skin.....	0	1	2	3	4
EYES AND MOUTH:		Not at all	Slightly	Moderately	Quite a bit	Extremely
6.	Dry eyes.....	0	1	2	3	4
7.	Need to use eye drops frequently.....	0	1	2	3	4
8.	Difficulty seeing clearly.....	0	1	2	3	4
9.	Need to avoid certain foods due to mouth pain.....	0	1	2	3	4
10.	Ulcers in mouth.....	0	1	2	3	4
11.	Receiving nutrition from an intravenous line or feeding tube.....	0	1	2	3	4
BREATHING:		Not at all	Slightly	Moderately	Quite a bit	Extremely
12.	Frequent cough.....	0	1	2	3	4
13.	Colored sputum.....	0	1	2	3	4
14.	Shortness of breath with exercise.....	0	1	2	3	4
15.	Shortness of breath at rest.....	0	1	2	3	4
16.	Need to use oxygen.....	0	1	2	3	4

EATING AND DIGESTION:		Not at all	Slightly	Moderately	Quite a bit	Extremely
17.	Difficulty swallowing solid foods.....	0	1	2	3	4
18.	Difficulty swallowing liquids.....	0	1	2	3	4
19.	Vomiting.....	0	1	2	3	4
20.	Weight loss.....	0	1	2	3	4
MUSCLES AND JOINTS:		Not at all	Slightly	Moderately	Quite a bit	Extremely
21.	Joint and muscle aches.....	0	1	2	3	4
22.	Limited joint movement.....	0	1	2	3	4
23.	Muscle cramps.....	0	1	2	3	4
24.	Weak muscles.....	0	1	2	3	4
Energy:		Not at all	Slightly	Moderately	Quite a bit	Extremely
25.	Loss of energy.....	0	1	2	3	4
26.	Need to sleep more/take naps.....	0	1	2	3	4
27.	Fevers.....	0	1	2	3	4
MENTAL AND EMOTIONAL:		Not at all	Slightly	Moderately	Quite a bit	Extremely
28.	Depression.....	0	1	2	3	4
29.	Anxiety.....	0	1	2	3	4
30.	Difficulty sleeping.....	0	1	2	3	4

Source:

[http://www.uniklinikum-regensburg.de/imperia/md/content/kliniken-institute/haematologie-onkologie/gvhd/deutsch/lee-symptom\\_scale.pdf](http://www.uniklinikum-regensburg.de/imperia/md/content/kliniken-institute/haematologie-onkologie/gvhd/deutsch/lee-symptom_scale.pdf)

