1.6. Testing Procedure and Level of Significance in the primary analysis

To preserve the study wise type I error rate of 0.05, the primary and secondary endpoints will be tested based on a serial gatekeeping testing procedure at the two-sided significance level of 0.05 according to the hierarchical order specified below:

1. Response rate at 48 weeks
2. Time to withdrawal of all corticosteroids for treatment of cGVHD
3. Time to withdrawal of all ISTs, including corticosteroids for treatment of cGVHD (with the exception of ibrutinib/placebo)
4. Response rate at 24 weeks
5. Improvement in Lee cGVHD Symptom Scale at 2 consecutive visits
6. Proportion of subjects who achieve reduction of corticosteroids dose level to less than 0.15 mg/kg/d at 24 weeks sustained for at least 30 days

Since the number of deaths at the primary analysis is expected to be low, formal analysis for OS will be performed at the final analysis. However, summary of OS will be provided based on available data at the time of the primary analysis. Duration of response will be analyzed to support the response endpoints.

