Improvement in overall score on Lee cGVHD Symptom Scale	
Proportion of subjects who had Lee total score decreasing at least 7 points at 2 consecutive visits with no PD, relapse of underlying disease or start of subsequent cGVHD treatment.
 
Proportion of subjects who had Lee total score decreasing at least 7 points at any time during the study (not preceded by PD, relapse of underlying disease or start of subsequent cGVHD treatment)
	
Comparison of the proportions between the two arms will be performed using chi-square test.
 
Supportive: Summary of the proportions of subjects with at least 7 points improvement at any
	ITT

Endpoint	Definition	Analysis Method	Population
	Mean Lee scores overtime	time will be provided. Summary of mean Lee scores overtime and graphs by treatment arm will be provided	
Proportion of subjects who achieve reduction of corticosteroids dose level to less than 0.15 mg/kg/d at 24 weeks sustained for at least 30 days	Proportion of subjects with prednisone equivalent dose reduction to a level of less than 0.15 mg/kg/d for a duration of at least 30 days at 24 weeks Mean daily corticosteroid dosing overtime	Comparison of the proportions between the two arms will be performed using Chi-square test Supportive: Mean (95%CI) of daily corticosteroid dosing over time will be summarized and plotted by arm	ITT
Duration of response	The interval between the date of initial documentation of a response (PR or better), and the date of first documented evidence of progressive cGVHD, relapse of underlying disease, start of subsequent cGVHD treatment, or death for responders only.	DOR will be estimated by Kaplan-Meier methodology: median DOR and landmark estimates with 2-sided 95% CIs will be provided for each treatment arm. K-M plots will be provided	Responders include subjects with response at any time during study treatment
Overall Survival	Time from the date of randomization until the date of death due to any cause. All deaths observed at the time of the data extraction date will be considered as events. For subjects who were not known to have died at the time of the analysis, OS data will be censored at date last known alive.	Survival will be estimated by Kaplan-Meier methodology: median OS and landmark estimates with 2-sided 95% CIs will be provided for each treatment arm. Kaplan-Meier plots will be provided	ITT
Exploratory Endpoints			

Endpoint	Definition	Analysis Method	Population

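### The gated Lee responder test (step 5) does not use the baseline Lee score; stratifying on it is a cheap change likely to add a few points of power

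*Protocol*

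**What the plan says.** The Lee form in Protocol Appendix F instructs patients "By circling one (1) number per line, please indicate how much you have been bothered by the following problems in the past month". Each of its 30 items is scored from 0 to 4, so no item can go below 0.

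SAP Section 4, Table 2 defines the gated Lee endpoint as "Proportion of subjects who had Lee total score decreasing at least 7 points at 2 consecutive visits with no PD", relapse or new cGVHD treatment. The method is "Comparison of the proportions between the two arms will be performed using chi-square test", in the ITT population. Protocol Section 10.4.2 agrees: the proportion improving on the Lee scale "will be analyzed using the same method for the primary efficacy endpoint".

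SAP Section 1.6 lists "Improvement in Lee cGVHD Symptom Scale at 2 consecutive visits" fifth of six hypotheses, which are "tested based on a serial gatekeeping testing procedure at the two-sided significance level of 0.05".

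Protocol Section 8.1.1 schedules the Lee scale at Screening ("Perform at the same time as cGVHD assessment"), and Section 8.2.1.1 schedules it predose on Day 1 if it was not done then. Protocol Section 4 sets no minimum Lee score for entry.

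SAP Section 4 explains why the primary endpoint is analysed unstratified: few adolescents, and IWRS errors in two randomization factors. It gives no such reason for the Lee endpoint.

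**The concern.** A subject with a high starting score has more room to fall by 7 points than one with a low score. At the extreme, a subject starting below 7 fails in either arm but stays in the ITT denominator. If starting score predicts response, an unadjusted comparison leaves that variation in the test as noise, and a chance imbalance in baseline score between arms moves the result. A test that compares like with like on baseline removes much of this.

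The SAP's reasons for not stratifying the primary analysis do not carry over. They concern sparse or mis-entered randomization factors, whereas the Lee score is a measured questionnaire value that can be cut into categories of reasonable size.

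At stake is the chance of passing step 5 and, because the gate is serial, of being allowed to test step 6 (corticosteroid dose reduction at 24 weeks).

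**Working it through.** **1. The plan's own figure.** No power is stated for the Lee test. For the primary endpoint (30% vs 50%, two-sided 5%, 80% power):

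n per arm = [1.960·√(2·0.40·0.60) + 0.842·√(0.30·0.70 + 0.50·0.50)]² / 0.20² = (1.358 + 0.571)² / 0.04 = 93, or 186 in total.

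This matches SAP Section 1.4. At the 193 enrolled (97/96 assumed), the same contrast has 81.4% power.

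**2. Why baseline should predict a fall.** If r is the baseline to follow-up correlation, the slope of improvement on baseline is 1 − r·(follow-up SD / baseline SD). With equal SDs, r = 0.9, 0.7 and 0.5 give slopes of 0.1, 0.3 and 0.5.

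**3. Simple model, chi-square vs CMH on baseline quartiles.** Assumed: n = 193; baseline gamma with mean 25 and SD 14; residual SD of change 9; floor at 0; success is one improvement of at least 7; 25% vs 43%; 4,000 runs per setting. The right-hand columns add 25% of subjects who fail whatever their baseline.

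| Slope | Chi-square | CMH | Gain | Chi-square (25% fail) | CMH (25% fail) | Gain |
|---|---|---|---|---|---|---|
| 0.1 | 75.1% | 75.2% | 0.1 | 77.0% | 76.5% | −0.5 |
| 0.2 | 74.4% | 75.9% | 1.5 | 76.6% | 77.4% | 0.8 |
| 0.3 | 75.2% | 78.6% | 3.4 | 77.8% | 79.6% | 1.8 |
| 0.5 | 77.0% | 85.6% | 8.6 | 76.1% | 80.9% | 4.8 |

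The Monte Carlo standard error of one power figure is √(0.75·0.25/4000) = 0.7 points.

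**4. Is the floor responsible?** Under this baseline distribution only 4.7% of subjects start below 7. Separate runs of the same model:

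- Floor on, slope 0: chi-square 75.1%, CMH 74.5%. No gain.
- Slope 0.3: 75.6% to 79.6% with the floor, 75.8% to 79.4% without it.
- Slope 0.5: 76.6% to 85.1% with the floor, 77.0% to 85.0% without it.

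The gain therefore comes from the baseline-change association. The floor matters by itself only if many subjects start low: with 20% unable to respond and no other baseline effect (30% vs 50%), chi-square gives 82.6% and CMH 86.3%.

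**5. Model with the two-visit rule.** Five post-baseline visits, scores floored at 0, a fall of at least 7 at two consecutive visits, 30% vs 50%, 2,000 runs. The adjusted test is a logistic likelihood-ratio test on continuous baseline. Events, where included, stop a subject from qualifying afterwards (assumed 12% per visit).

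| Baseline mean / SD, r | No events | With events |
|---|---|---|
| 15 / 10, 0.50 | 81.5% to 90.6% | 83.8% to 89.2% |
| 22 / 13, 0.50 | 80.6% to 87.7% | 82.0% to 85.9% |
| 22 / 13, 0.70 | 81.2% to 86.3% | 81.6% to 84.1% |
| 22 / 13, 0.85 | 81.8% to 84.9% | 81.8% to 83.5% |
| 30 / 15, 0.85 | 81.1% to 83.5% | 82.6% to 82.9% |

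The middle row gains 5.1 points without events and 2.5 with them. Over the full grid the gain runs from 0.3 to 9.1 points.

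**6. CMH against a continuous covariate.** In a third, logistic model (30% vs 50%; log-odds slope 1.0 per baseline SD), chi-square has 82.7% power, logistic adjustment 88.6% and CMH on quartiles 87.3%. Quartiles keep 4.6 of the 5.9 points. At the extreme slope of 1.5 the figures are 80.1%, 91.6% and 89.7%. With slope 0 and about 5% of subjects unable to respond, CMH is about one point worse (82.0% vs 81.0%).

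**7. Type I error.** It is 4.6% to 5.4% in the simple model. In the two-visit model it is 4.3% to 5.7% for chi-square and 4.5% to 5.7% adjusted.

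**The case against.** The strongest reply is that nothing here is an error. Randomization makes the chi-square valid. It is simple, gives a marginal comparison, needs no rule for a missing baseline, matches the other gated proportions and follows Protocol Section 10.4.2. All of that stands. Baseline is also not absent from the endpoint, because the outcome is itself a fall in score; only the test leaves it out.

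A second reply is that the size is unknown. The documents give no baseline Lee mean or SD, no link between baseline and change, and no assumed Lee effect. The only Lee responder figure is 24% (10/42) in Protocol Section 1.2.5, from a single-arm study after steroid failure. This also stands: the gain can be nil, and the largest gains need a strong association. Against that, a slope as low as 0.1 needs a correlation of about 0.9 (with equal SDs) over months in which every subject starts new systemic treatment, so some gain is more plausible than none.

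A third reply is that step 5 is reached only if steps 1 to 4 all succeed, and step 1 alone was sized at 80%. That reduces the overall effect. If the gain did not depend on the earlier results, 5 points at step 5 would be at most about 0.80 × 5 = 4 points overall.

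A reader might infer that the form's floor of 0 is what costs the power. The calculation does not support that: removing the floor leaves the gain almost unchanged.

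**Conclusion.** The point holds as a cheap improvement. The step 5 test leaves out a baseline score that is scheduled before treatment and is likely to predict response, and no section gives a reason for leaving it out. With 193 subjects and 25% vs 43% or 30% vs 50%, using baseline adds about 2 to 5 points of power in middle settings, with a range from 0 to about 9 and type I error near 5%. These figures depend on the assumed Lee distribution, correlation and response rates, none of which the documents supply. The consequence is limited to steps 5 and 6, and arises only once steps 1 to 4 have succeeded.

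Two stronger readings are not supported. One is that the test is biased or invalid; it is neither. The other is that power is certainly lost for no return. The loss may be close to zero if baseline is weakly prognostic, and the crude test does buy simplicity.

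**What to change.** Before unblinding, in the Lee row of SAP Table 2:

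- Replace the chi-square with a CMH test stratified by baseline Lee total score, in four categories set on blinded pooled data.
- Put subjects with a missing baseline in their own stratum, so that the ITT denominator is kept.
- Report the Mantel-Haenszel risk difference with its 95% CI, and keep the crude chi-square as supportive.
- State how the 30 items form the total score and which visit is the reference for the fall. The SAP gives neither, and the strata depend on both.

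The 7-point definition, the ITT population and the place in the hierarchy stay as they are. SAP Section 1.7.1 says the sponsor is blinded, so the categories can still be set without knowledge of treatment.

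The cost is a few words in the SAP and a line of code. The downsides are the missing-baseline rule, and little or no gain (possibly a loss of about one point) if baseline turns out to be weakly prognostic.

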## Appendix G. SF-36 Questionnaire

## Your Health and Well-Being

This survey asks for your views about your health. This information will help keep track of how you feel and how well you are able to do your usual activities. Thank you for completing this survey!

For each of the following questions, please mark an  in the one box that best describes your answer.

1. In general, would you say your health is:

Excellent	Very good	Good	Fair	Poor
▼	▼	▼	▼	▼
 1	 2	 3	 4	 5

2. Compared to one year ago, how would you rate your health in general now?

Much better now than one year ago	Somewhat better now than one year ago	About the same as one year ago	Somewhat worse now than one year ago	Much worse now than one year ago
▼	▼	▼	▼	▼
 1	 2	 3	 4	 5

SF-36v2® Health Survey © 1992, 1996, 2000 Medical Outcomes Trust and QualityMetric Incorporated. All rights reserved.  
SF-36® is a registered trademark of Medical Outcomes Trust.  
(SF-36v2® Health Survey Standard, United States (English))

**3. The following questions are about activities you might do during a typical day. Does your health now limit you in these activities? If so, how much?**

Yes, limited a lot	Yes, limited a little	No, not limited at all
▼	▼	▼

- a. Vigorous activities, such as running, lifting heavy objects, participating in strenuous sports .....  1 .....  2 .....  3
- b. Moderate activities, such as moving a table, pushing a vacuum cleaner, bowling, or playing golf .....  1 .....  2 .....  3
- c. Lifting or carrying groceries .....  1 .....  2 .....  3
- d. Climbing several flights of stairs .....  1 .....  2 .....  3
- e. Climbing one flight of stairs .....  1 .....  2 .....  3
- f. Bending, kneeling, or stooping .....  1 .....  2 .....  3
- g. Walking more than a mile .....  1 .....  2 .....  3
- h. Walking several hundred yards .....  1 .....  2 .....  3
- i. Walking one hundred yards .....  1 .....  2 .....  3
- j. Bathing or dressing yourself .....  1 .....  2 .....  3

SF-36v2® Health Survey © 1992, 1996, 2000 Medical Outcomes Trust and QualityMetric Incorporated. All rights reserved.  
SF-36® is a registered trademark of Medical Outcomes Trust.  
(SF-36v2® Health Survey Standard, United States (English))

**4. During the past 4 weeks, how much of the time have you had any of the following problems with your work or other regular daily activities as a result of your physical health?**

	All of the time	Most of the time	Some of the time	A little of the time	None of the time
a. Cut down on the amount of time you spent on work or other activities .....	 1	 2	 3	 4	 5
b. Accomplished less than you would like .....	 1	 2	 3	 4	 5
c. Were limited in the kind of work or other activities .....	 1	 2	 3	 4	 5
d. Had difficulty performing the work or other activities (for example, it took extra effort) .....	 1	 2	 3	 4	 5

**5. During the past 4 weeks, how much of the time have you had any of the following problems with your work or other regular daily activities as a result of any emotional problems (such as feeling depressed or anxious)?**

	All of the time	Most of the time	Some of the time	A little of the time	None of the time
a. Cut down on the amount of time you spent on work or other activities .....	 1	 2	 3	 4	 5
b. Accomplished less than you would like .....	 1	 2	 3	 4	 5
c. Did work or other activities less carefully than usual .....	 1	 2	 3	 4	 5

SF-36v2® Health Survey © 1992, 1996, 2000 Medical Outcomes Trust and QualityMetric Incorporated. All rights reserved.  
SF-36® is a registered trademark of Medical Outcomes Trust.  
(SF-36v2® Health Survey Standard, United States (English))

6. During the past 4 weeks, to what extent has your physical health or emotional problems interfered with your normal social activities with family, friends, neighbors, or groups?

Not at all	Slightly	Moderately	Quite a bit	Extremely
▼	▼	▼	▼	▼
 1	 2	 3	 4	 5

7. How much bodily pain have you had during the past 4 weeks?

None	Very mild	Mild	Moderate	Severe	Very severe
▼	▼	▼	▼	▼	▼
 1	 2	 3	 4	 5	 6

8. During the past 4 weeks, how much did pain interfere with your normal work (including both work outside the home and housework)?

Not at all	A little bit	Moderately	Quite a bit	Extremely
▼	▼	▼	▼	▼
 1	 2	 3	 4	 5

SF-36v2® Health Survey © 1992, 1996, 2000 Medical Outcomes Trust and QualityMetric Incorporated. All rights reserved.  
SF-36® is a registered trademark of Medical Outcomes Trust.  
(SF-36v2® Health Survey Standard, United States (English))

9. These questions are about how you feel and how things have been with you during the past 4 weeks. For each question, please give the one answer that comes closest to the way you have been feeling. How much of the time during the past 4 weeks...

	All of the time	Most of the time	Some of the time	A little of the time	None of the time
a Did you feel full of life? .....	 1	 2	 3	 4	 5
b Have you been very nervous? .....	 1	 2	 3	 4	 5
c Have you felt so down in the dumps that nothing could cheer you up? .....	 1	 2	 3	 4	 5
d Have you felt calm and peaceful? .....	 1	 2	 3	 4	 5
e Did you have a lot of energy? .....	 1	 2	 3	 4	 5
f Have you felt downhearted and depressed? .....	 1	 2	 3	 4	 5
g Did you feel worn out? .....	 1	 2	 3	 4	 5
h Have you been happy? .....	 1	 2	 3	 4	 5
i Did you feel tired? .....	 1	 2	 3	 4	 5

10. During the past 4 weeks, how much of the time has your physical health or emotional problems interfered with your social activities (like visiting with friends, relatives, etc.)?

All of the time	Most of the time	Some of the time	A little of the time	None of the time
 1	 2	 3	 4	 5

SF-36v2® Health Survey © 1992, 1996, 2000 Medical Outcomes Trust and QualityMetric Incorporated. All rights reserved.  
SF-36® is a registered trademark of Medical Outcomes Trust.  
(SF-36v2® Health Survey Standard, United States (English))

11. How TRUE or FALSE is each of the following statements for you?

	Definitely true	Mostly true	Don't know	Mostly false	Definitely false
a I seem to get sick a little easier than other people .....	 1	 2	 3	 4	 5
b I am as healthy as anybody I know .....	 1	 2	 3	 4	 5
c I expect my health to get worse .....	 1	 2	 3	 4	 5
d My health is excellent .....	 1	 2	 3	 4	 5

*Thank you for completing these questions!*

SF-36v2® Health Survey © 1992, 1996, 2000 Medical Outcomes Trust and QualityMetric Incorporated. All rights reserved.  
SF-36® is a registered trademark of Medical Outcomes Trust.  
(SF-36v2® Health Survey Standard, United States (English))

